6.8. End of Study or Early Termination Visit

Each subject's participation in the study will end once the subject experiences a first sJIA flare in the double-blind phase or 24 consecutive weeks of inactive disease (clinical remission). An end-of-study visit should be performed.

Subjects who are not able to maintain an Adapted JIA ACR 30 response for 4 weeks in the open-label phase, or who have fever due to sJIA lasting more than 2 consecutive days in Part 1, or who fail CS tapering more than twice in Part 2 of the open-label phase will need to be discontinued from the study.

Subjects will have the option, if eligible (based on inclusion and exclusion criteria), of enrolling in the tofacitinib JIA long-term extension study (A3921145) after withdrawal or completion of this study.

- Subjects who discontinue investigational product in the double-blind phase and who do not enter A3921145 will be required to continue in the study and perform all scheduled visits until Week 52 after randomization or until the study concludes, whichever comes first. Such subjects should transition to standard-of care treatment in accordance with local guidelines.
- Subjects who discontinue in the Open-Label Phase and do not enter A3921145 will be required to return for a follow up visit 28 days after the last dose of study treatment.

The study will be completed once the requisite number of subjects have reported flare in the double-blind withdrawal phase (refer to [Section 11](#)). At that time and upon notification by the Sponsor, the investigator will be required to schedule an end-of-study visit for all remaining active subjects.

If a subject discontinues from the study at a regularly scheduled study visit, all assessments and procedures for that visit should be completed. In addition, a Tanner stage assessment should be done as part of the study termination. If a subject discontinues outside of a regularly scheduled visit, an Early Termination visit should be scheduled as soon as possible. The procedures and assessments listed below will be performed at the End of Study or Early Termination visit.

Subjects should be instructed to fast, if possible, for lipid panel testing.

- Review concomitant medications. Refer to [Section 5.8](#).
- Complete physical exam, including skin examination for chickenpox or shingles. **Country specific amendment for EU sites (including UK):** a full skin cancer examination must be performed as part of the complete physical examination.

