6.9. Follow-Up Visit (Only For Subjects Not Entering Study A3921145)

At least 28 days after the last dose of study medication, subjects who did not rollover into study A3921145 will return for a follow-up visit. This visit will not be required for subjects who discontinue investigational product in the double-blind phase and remain in the study. There is a +7 day window for this visit. The procedures and assessments listed below will be performed at this visit:

- Review concomitant medications. Refer to [Section 5.8](#).
- Targeted physical exam, including skin examination for chickenpox or shingles.
- Perform a risk factor check for venous thromboembolism. Refer to [Section 8.2.13](#) for details.
- Vital signs, height and weight.
- **For females of childbearing potential:** Obtain blood (serum) or urine sample for local laboratory pregnancy testing.
- **For subjects using contraception:** perform a contraceptive check, to ensure contraception is consistently and correctly used.
- Assess for adverse events.
- **Only if subject discontinued in the double-blind phase for other reasons than “flare” per protocol before Week 24 (of the double-blind phase):**
 - Review temperature diary and assess “Fever” and “Absence of fever”;
 - Obtain subject’s oral temperature and assess “Fever”, defined as temperature $>38^{\circ}\text{C}/100.4^{\circ}\text{F}$.
 - **MAS diagnosis: Only if subject has fever and MAS is suspected:** obtain blood samples to evaluate Ferritin, Platelets, Triglycerides and Fibrinogen levels. Refer to [Section 8.2.11](#) for details regarding these blood sample collections;

- Evaluate “Absence of fever”, defined as documented absence of fever due to systemic JIA in the week preceding this visit. Record the outcome in the eCRF for calculation of the Adapted JIA ACR response.
- Assess the sJIA Disease Activity status:
 - Fever (see above);
 - Number of joints with limitation in range of motion;
 - Number of joints with active arthritis (swelling and/or pain/tenderness);
 - Assess duration of morning stiffness;
 - Assess extra-articular sJIA manifestations: rash, serositis, splenomegaly, hepatomegaly, or generalized lymphadenopathy attributable to sJIA;
 - Uveitis status: document presence/absence of active uveitis;
 - Physician’s Global Assessment of Overall Disease Activity;
 - Administer the Childhood Health Assessment Questionnaire (CHAQ); evaluate Patient wellbeing as part of the CHAQ on a 21 circle VAS;

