14.2. End of Trial in All Other Participating Countries

End of trial in all other participating countries is defined as Last Subject Last Visit (LSLV).

Last subject last visit (LSLV) is defined as the date the investigator reviews the last subject's final safety data and determines that no further evaluation is required for the subject to complete the trial.

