## 2.3. Estimands

### 2.3.1. Primary Estimand

The primary estimand (Estimand 1) of this study is a composite estimand (accounting for both treatment adherence and response), defined according to the primary objective and in alignment with the primary endpoint. It includes the following 5 attributes:

- Population: sJIA patients, as defined by the inclusion criteria for the double-blind phase, who are randomized.
- Treatment: tofacitinib 5 mg BID, placebo

- Variable: time to sJIA disease flare in the double-blind phase.

Patients who complete study participation after maintaining JIA ACR inactive disease for at least 24 weeks (ie, clinical remission) in the double-blind phase, and patients who are still active in the double-blind withdrawal phase of the study but have to discontinue due to study end, will be considered as non-flare and censored at the last available flare assessment while on investigational product. (More details of on-treatment censoring time and risk period are provided in [Section 5.3.1.1](#).)

Patients who discontinue from investigational product for any other reasons are considered as having a disease flare on the investigational product discontinuation day.

- Intercurrent event: investigational product discontinuation is the intercurrent event. The intercurrent event is captured through the variable definition. Data collected after discontinuation of the investigational product (ie, off-treatment data) will not be included to derive the endpoint, ie, only on-treatment data will be used. (See [Appendix 3.13](#) for definition of on-treatment data.)
- Population-level summary: hazard ratio of disease flare for those assigned to tofacitinib at randomization versus those assigned to placebo at randomization in the double-blind phase.

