#### On-Treatment Censoring Time and Risk Period

The risk period corresponding to the on-treatment censoring time is defined from the date of the randomization to the minimum of (last contact date, last investigational product dose date + 2 days). The addition of 2 days to the last investigational product dose date permits the data collected 2 days after the last investigational product dose be considered as on-treatment. Explicitly, the risk period is calculated as the minimum of (last contact date, last investigational product dose date + 2 days) – date of randomization + 1.

This risk period will be used in the primary analysis (Estimand 1) and a supplementary analysis (Estimand 4) for time to disease flare.

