### **6.1.2.2. Sensitivity Analyses: Tipping Point Analysis**

#### Sensitivity Analysis 1

This analysis will be performed only when superiority is achieved based on the primary analysis for the primary endpoint ([Section 6.1.1](#)).

The impact of missing data (ie, censoring) on the primary analysis (composite estimand) will be evaluated through model-based multiple imputation. For subjects who are censored under the composite estimand, the imputation will be done to the LSLV of Study A3921165. Imputation model will be fit for patients assigned to tofacitinib and placebo.

Tipping point analysis will be conducted to explore the plausibility of missing data assumptions under which the conclusions change, i.e., under which there is no longer evidence of a treatment effect. The tipping point analysis will be two-dimensional, i.e., will allow assumptions about the censored times on the two arms to vary independently.

In the tipping point analysis approach, the post-censoring hazard of flares for subjects with censored time to flare will be varied over a grid of sensitivity parameters that increase or decrease the hazard function relative to the CAR (censoring at random) analysis in both the tofacitinib and placebo groups.

The primary endpoint is time to disease flare in the double-blind phase. Patients who are censored without disease flare contribute partial information about the endpoint, which can be analyzed using standard statistical methods for survival data. Weibull regression model will be fit for both observed and censored data as the imputation model. Statistical simulations were conducted suggesting estimation bias for Weibull parameters was minimal when the Weibull shape parameter was  $\geq 1$ . The assumed Weibull shape parameter of 1 was supported by data of a prior completed pJIA study (A3921104). Conditional on the observed

censored time, a time-to-flare will be imputed, subject to the end-of-study constraint as follows: use the imputed time-to-flare if the imputed time-to-flare is prior to the end of study (ie, LSLV of Study A3921165); but censored at the end of the study, if the imputed time-to-flare exceeds the LSLV date of Study A3921165.

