**Step 4: Impute the time-to-event under a CNAR assumption ( $c$ ) using the sampled Weibull parameters.**

For subject  $i$  with censored time-to-event (ie,  $\delta_i = 1$ ) and with a specified CNAR sensitivity parameter  $c$ , using a single set of sampled Weibull parameters  $(\gamma_i^*, k^*)$  in Step 2, we can reconstruct the conditional predictive distribution as follows:

$$\gamma_i^{c*} = \gamma_i^* / (c^{1/k^*})$$

$$F_i^{c*}(t_i | t_i > T_i; c, \gamma_i^*, k^*) = 1 - \exp \left[ \left( \frac{T_i}{\gamma_i^{c*}} \right)^{k^*} - \left( \frac{t_i}{\gamma_i^{c*}} \right)^{k^*} \right].$$

In order to impute  $t_i$  (imputed value as  $t_i^*$ ), we generate one  $u_i^* \sim \text{Uniform}(0,1)$  for subject  $i$ , then we can solve for  $t_i^*$ ,

$$t_i^* | t_i > T_i = \gamma_i^{c*} \left[ \left( \frac{T_i}{\gamma_i^{c*}} \right)^{k^*} - \log(1 - u_i^*) \right]^{1/k^*}.$$

Different CNAR sensitivity parameter ( $c$ ) values will give different imputed  $t_i^*$  using the same  $u_i^*$  for this subject  $i$ .

The risk period and censoring time for imputation are defined for Sensitivity Analysis 1 and Sensitivity Analysis 2 separately:

Sensitivity Analysis 1:

The risk period for imputation is defined from the date of the randomization to the LSLV of Study A3921165, for subjects who are censored under the composite estimand.

Sensitivity Analysis 2:

- 1) the risk period for imputation is defined from the date of the randomization to the LSLV of Study A3921165, for subjects who are censored under the treatment policy estimand and not enrolled in the LTE study (Study A3921145);
- 2) the risk period for imputation is defined from the date of the randomization to the LSLV of Study A3921165 or to Randomization Day + 378 (the upper limit of the DB Week 52 visit window), whichever comes later, for subjects who are censored under the treatment policy estimand and enrolled in the LTE study (Study A3921145). “Randomization Day + 378” will include time spent post randomization in both Study A3921165 and Study A3921145. For example, if a subject is randomized on Study Day 80, then “Randomization Day + 378” is Study Day 458 and DB Phase Day 379; so imputation will be done up to max (LSLV of A3921165 – date of randomization + 1, DB Phase Day 379) for this subject enrolled in Study A3921145.

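### The tipping-point analysis imputes flares past study end for children whose on-treatment follow-up is already complete

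*Protocol*

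**What the plan says.** SAP 2.3.1 censors two groups under Estimand 1: children who complete in clinical remission, and "patients who are still active in the double-blind withdrawal phase of the study but have to discontinue due to study end". Both are "censored at the last available flare assessment while on investigational product". SAP 5.3.1.1 ends the on-treatment risk period at the "minimum of (last contact date, last investigational product dose date + 2 days".

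SAP 6.1.2.2 sets the window for Sensitivity Analysis 1: "For subjects who are censored under the composite estimand, the imputation will be done to the LSLV of Study A3921165". Appendix 5, Step 4 repeats it: "The risk period for imputation is defined from the date of the randomization to the LSLV of Study A3921165". Neither place exempts children censored by study end. A drawn time beyond LSLV is re-censored at LSLV. The analysis runs only after a positive primary result.

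The SAP uses LSLV without defining it. The only definition in either document is in Protocol 14.2: "Last subject last visit (LSLV) is defined as the date the investigator reviews the last subject's final safety data". Two other protocol rules bear on the date. Section 6.8 says that once the flare target is met, "upon notification by the Sponsor, the investigator will be required to schedule an end-of-study visit for all remaining active subjects". Section 6.9 adds: "At least 28 days after the last dose of study medication, subjects who did not rollover into study A3921145 will return for a follow-up visit".

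**The concern.** A tipping-point analysis asks how far the hazard of children with unseen outcomes would have to depart from the model before the conclusion fails. A child who is flare-free on product when the event target closes the study was followed as planned. Stopping there is administrative censoring and carries no information about prognosis.

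For such a child, the time from their own end-of-study visit to LSLV lies outside the Estimand 1 risk period. A flare drawn there could not have been counted had it really occurred. The length of this interval is set by visit scheduling, by whether any child declines the extension, and by how fast sites close. The robustness statement attached to a positive result would then depend partly on close-out logistics. Most of these children are on tofacitinib, so a multiplier applied to that arm weakens the observed effect.

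**Working it through.** **1. The plan's own figure.** Inputs (SAP 5.1 and Table 2): HR 0.36, one-sided alpha 0.025, 28 flares at the First and 37 at the Final Analysis, gamma 4 for efficacy and -4 for futility. Alpha spent at the First Analysis = 0.025 × (1 − e^(−4×28/37)) / (1 − e^(−4)) = 0.0242. The boundaries are z = −1.973 and −2.586 (HR 0.474 and 0.427). With drift ln(0.36)·√D/2 (D = number of flares), power is 80.4%. All of this matches Table 2. The documents give no figure for the imputation window.

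**2. Length of the interval.** If a child does not roll over, LSLV is at least 28 days after that child's last dose. Section 6.9 allows +7 days, giving 28 to 35 days. (The Schedule of Activities prints ±7 days; the Section 6.9 wording is used here.) If all children roll over and the review is prompt, the gap can be near zero.

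**3. Chance of an imputed flare per child.** With Weibull shape 1, the value SAP 6.1.2.2 assumes, P = 1 − exp(−c·h·g). Here g is the gap in days and c the multiplier of Appendix 5, Step 3. The daily hazard h is ln 2/236 = 0.00294 on placebo and 0.36 × 0.00294 = 0.00106 on tofacitinib.

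| Gap | c = 1, placebo / tofacitinib | c = 5, tofacitinib |
|---|---|---|
| 7 days | 2.0% / 0.7% | 3.6% |
| 28 days | 7.9% / 2.9% | 14% |
| 35 days | 9.8% / 3.6% | 17% |
| 63 days | 17% / 6.4% | 28% |

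**4. Number of imputed flares.** Simulating 54 children with the accrual in Protocol 10.1.1, stopped at flare 37 with no remission exits, leaves on average 11.8 tofacitinib and 4.9 placebo children censored by study end. At 35 days and c = 1 the expected count is 11.8 × 0.036 + 4.9 × 0.098 = 0.9 flares. At tofacitinib c = 5 and placebo c = 1 it is 11.8 × 0.169 + 4.9 × 0.098 = 2.5. Mean log-rank z among positive trials moves from −3.21 to −3.25 at c = 1 and −3.07 at c = 5. Even at c = 10 (4.2 flares) it is −2.88, still beyond −2.586. The average trial does not tip; those near the boundary can.

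**5. How often significance is lost.** Positive trials under the two-look design were imputed with placebo multiplier 1 and no remission exits. The log-rank z was pooled by Rubin's rules and compared with the boundary crossed. There were about 1,160 positive trials and 40 imputations for multipliers 2 to 5; the multiplier 1 column comes from a separate run of 500 positive trials.

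| Horizon past data cut | ×1 | ×2 | ×3 | ×5 |
|---|---|---|---|---|
| 0 days | 0% | 0% | 0% | 0% |
| 35 days | about 1% | 5% | 9% | 15% |
| 70 days | about 1% | 8% | 14% | 25% |
| 180 days | about 2% | 14% | 25% | 42% |

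The first row is zero by construction, since nothing is imputed. A separately coded run (700 positive trials, 25 imputations) gave 4%, 9% and 17% at 35 days for multipliers 2, 3 and 5. The SAP pools Wilson-Hilferty-transformed chi-squares, not z, so these rates are approximate.

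**6. Scale of the multipliers.** 1/0.36 = 2.78, so a tofacitinib multiplier above 2.78 assumes flaring faster than on placebo.

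**The case against.** The strongest reply is that this is a conditional sensitivity analysis that changes no decision, that a longer horizon with adverse tofacitinib multipliers works against the sponsor, and that tipping only at multipliers above the placebo hazard is itself reassuring. All of that stands and limits the weight of the point. It does not explain why close-out time should enter the analysis.

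A reader might infer more than the documents support:

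- *Nobody is on blinded product in the gap.* Dosing continues until each child's end-of-study visit, which follows sponsor notification and will be staggered. After a stop at the First Analysis, much of the time between data cut and LSLV could be on product, so the 70- and 180-day rows are not estimates of off-product time. Children who roll over may also be taking open-label tofacitinib.
- *Every such child is given a flare.* Draws past LSLV are re-censored, and at multiplier 1 few children receive one.
- *The safety-review wording is the cause.* Protocol 14.2 covers non-EU countries and the SAP does not cite it. A literal last visit would still include the 28-day follow-up. The cause is the missing exemption.
- *The analysis mainly stresses administrative censoring.* This is not shown. Remission completers can be imputed over much longer intervals: over 100 weeks at multiplier 1, 87% on placebo and 52% on tofacitinib would be given a flare.
- *Nothing at all is unobserved.* Censoring is at the last on-product assessment, and visits are four weeks apart, so a short stretch before study end may be unassessed.
- *The same argument applies to Sensitivity Analysis 2.* Estimand 5 deliberately counts off-treatment flares, so the on-treatment objection does not carry over.

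**Conclusion.** The point holds for Sensitivity Analysis 1. As written, children censored only because the study ended can receive flares that Estimand 1 could not count, in an interval whose length depends on close-out. The effect is slight at multiplier 1 and becomes material at adverse multipliers, mostly in trials already near the boundary.

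The size rests on assumptions: the gap length, the multipliers (Appendix 5 leaves the grid to the programming plan), shape 1, and no remission exits. With remission exits, fewer children are censored by study end. If 20% could leave in remission, about 10 remain and a 35-day gap yields 0.5 imputed flares at multiplier 1. The documents give no ground for doubting the primary result, type I error control or power.

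**What to change.** In SAP 6.1.2.2 and Appendix 5, Step 4:

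1. Leave subjects censored because the study ended at their last on-product flare assessment, without imputation; or cap their imputation at their own end-of-study visit.
2. Impute only clinical-remission completers, and end their imputation at the data cut-off of the analysis being tested, in place of LSLV. State that this is a deliberate what-if, because their time after exit is also off blinded product.
3. In Sensitivity Analysis 2, use the same cut-off on the ground that no follow-up is planned after study end. Keep the Randomization Day + 378 limit for extension participants.

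The change affects SAP and programming-plan wording only. The cost is a stress test on fewer children, which may be hard to tip if few leave in remission. It would not be empty: if 15% could leave in remission (assumption), 6%, 8% and 12% of simulated positive trials lose significance at multipliers 2, 3 and 5 with the horizon at the data cut.

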15. SPONSOR DISCONTINUATION CRITERIA

Premature termination of this study may occur because of a regulatory authority decision, change in opinion of the IRB/EC, investigational product safety problems, or at the discretion of Pfizer. In addition, Pfizer retains the right to discontinue development of tofacitinib at any time.

If a study is prematurely terminated or discontinued, Pfizer will promptly notify the investigator. After notification, the investigator must contact all participating subjects and the hospital pharmacy (if applicable) within 7 days. As directed by Pfizer, all study materials must be collected and all CRFs completed to the greatest extent possible.

16. PUBLICATION OF STUDY RESULTS

16.1. Communication of Results by Pfizer

Pfizer fulfills its commitment to publicly disclose clinical trial results through posting the results of studies on www.clinicaltrials.gov (ClinicalTrials.gov), the European Clinical Trials Database (EudraCT), and/or www.pfizer.com, and other public registries in accordance with applicable local laws/regulations.

In all cases, study results are reported by Pfizer in an objective, accurate, balanced, and complete manner and are reported regardless of the outcome of the study or the country in which the study was conducted.

www.clinicaltrials.gov

Pfizer posts clinical trial US Basic Results on www.clinicaltrials.gov for Pfizer-sponsored interventional studies conducted in subjects that evaluate the safety and/or efficacy of a Pfizer product, regardless of the geographical location in which the study is conducted. US Basic Results are submitted for posting within 1 year of the primary completion date for studies in adult populations or within 6 months of the primary completion date for studies in pediatric populations.

Primary completion date is defined as the date that the final subject was examined or received an intervention for the purposes of final collection of data for the primary outcome, whether the clinical study concluded according to the prespecified protocol or was terminated.

EudraCT

Pfizer posts EU Basic Results on EudraCT for all Pfizer-sponsored interventional studies that are in scope of EU requirements. EU Basic Results are submitted for posting within 1 year of

the primary completion date for studies in adult populations or within 6 months of the primary completion date for studies in pediatric populations.

[www\(pfizer.com](http://www(pfizer.com)

Pfizer posts Public Disclosure Synopses (clinical study report synopses in which any data that could be used to identify individual subjects has been removed) on [www\(pfizer.com](http://www(pfizer.com) for Pfizer-sponsored interventional studies at the same time the US Basic Results document is posted to www.clinicaltrials.gov.

